CONCERN intervention trial data collection and analysis includes collection of pre and post-intervention data during the 6 months before the intervention and 12 months after the intervention (see **Error! Reference source not found.** for timeline). Prior to conducting hypotheses tests, descriptive statistics will be used to describe outcome variables and key confounding variables. We propose a generalized linear mixed model to examine the impact of the CONCERN system on each of the two primary outcomes: in-hospital mortality and length of stay. This model is used to deal with combined data from multiple sites and can account for changes over time. This model allows different baselines and trajectories for different ICUs and non-ICU settings and can include both patient level and unit level covariates. We will also use a generalized linear mixed model for an interrupted time series analysis for unit level analysis. We will include a variable for closed versus open units in our analysis. We estimated statistical power for the comparison of mortality rates between the intervention and non-intervention periods and between silent and active model periods. All power calculations were based on 2-sided tests with alpha = 0.05. Using hospital patients' statistics, we expected at least 2,000 total admissions per month (ranging from 38 to 270 admissions in different units) with a mean mortality rates of 37.5 deaths per 10,000 inpatient days (ranging from 11.9 to 48.8), see Table 1. Using a very conservative number of total 50,000 inpatient days in each intervention period, we will have at least 80% statistical power to detect a difference of less than 1% relative difference in mortality rates. Because the 1% change in mortality are smaller than a clinically meaningful difference, we should have sufficient sample size. When examined by different campuses, using a very conservative value of inpatient days in one campus of 6000 inpatient days in each intervention period, we will have at least 80% statistical power to detect a difference of less than 2% relative difference in mortality rates. There is no consensus regarding the best method for analyzing length of stay. Length of stay has been analyzed using both Poisson models (or NB, or other related models such as Zero-truncated Poisson models) and survival models (such as Cox PH models).¹¹⁹ Both approaches will be applied to length of stay and the better performing model will be retained. We will use the logit link function for 30-day hospitalization outcomes. We will calculate the Number Needed to Treat during the months when the CONCERN system is on silent mode and in active mode for the non-ICU versus ICU and at each site for the

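### The mortality power statement is wrong as written: power for the stated 1% and 2% relative differences is about 5%, and 80% power needs reductions of about 27% and 68%

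*Combined protocol and SAP*

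**What the plan says.** The power argument is in Section 1 of the combined protocol and SAP, in the paragraph on intervention trial data collection and analysis. It covers the "comparison of mortality rates between the intervention and non-intervention periods and between silent and active model periods". On the error rate it says "All power calculations were based on 2-sided tests with alpha = 0.05". The baseline is given as "mean mortality rates of 37.5 deaths per 10,000 inpatient days (ranging from 11.9 to 48.8" per 10,000 days across sites, with a pointer to Table 1.

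Two claims follow:

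- Overall, at an exposure of 50,000 days a period, the claim is: "we will have at least 80% statistical power to detect a difference of less than 1% relative difference in mortality rates".
- For a single campus, at an exposure of 6,000 days a period, the claim is: "we will have at least 80% statistical power to detect a difference of less than 2% relative difference in mortality rates".

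Between the two, the plan concludes: "Because the 1% change in mortality are smaller than a clinically meaningful difference, we should have sufficient sample size".

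It gives no formula, no allowance for clustering, and no value for a clinically meaningful mortality difference.

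**The concern.** A 1% relative change on 187.5 expected deaths is fewer than two deaths. A 2% change on 22.5 expected deaths is less than half a death. The Poisson standard deviation of a count of 187.5 is about 14 (√187.5 = 13.7), and of 22.5 about 5 (√22.5 = 4.7), so differences of that size cannot be told from chance.

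This paragraph is the only justification of sample size, and it concerns a primary outcome. The conclusion that the sample is sufficient rests wholly on the 1% figure. Anyone who takes the stated power at face value could read a non-significant mortality result as evidence against an effect as small as 1%, when the data could not exclude far larger effects.

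**Working it through.** **Baseline rate.** The plan's rate can be reproduced from Table 1 as deaths / (beds × occupancy × 365):

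| Site | Bed-days | Deaths | Per 10,000 |
|---|---|---|---|
| PHS-BWH | 777 × 0.95 × 365 = 269,425 | 1,001 | 37.2 |
| PHS-NWH | 300 × 0.94 × 365 = 102,930 | 312 | 30.3 |
| NYP-CUMC | 745 × 0.95 × 365 = 258,329 | 1,261 | 48.8 |
| NYP-Allen | 300 × 0.75 × 365 = 82,125 | 98 | 11.9 |
| All | 712,809 | 2,672 | 37.5 |

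The mean and the range both match, so the unit is deaths per inpatient day and the inputs are being read correctly.

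**Expected deaths per period.** 50,000 × 0.00375 = 187.5. 6,000 × 0.00375 = 22.5.

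**Power at the stated differences.** For expected deaths d1 and d2 in equal periods, z = |d1 − d2| / √(d1 + d2) and power = Φ(z − 1.96) + Φ(−z − 1.96).

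- 50,000 days, 1%: d2 = 185.625, z = 1.875 / √373.125 = 0.097, power 5.1%.
- 6,000 days, 2%: d2 = 22.05, z = 0.45 / √44.55 = 0.067, power 5.05%.

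The plan states at least 80% for both.

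**Differences detectable with 80% power** (same formula, solved for the rate ratio).

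- 50,000 days: rate ratio 0.731, a 27% reduction (or 1.31 for an increase).
- 6,000 days: rate ratio 0.321, a 68% reduction (or 2.03 for an increase).

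Other methods agree. Square-root, log-rate and exact Poisson calculations all give about 27% at 50,000 days. At 6,000 days they give 66%, about 71% and 70%. One-sided testing would give 24% and 62%.

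**Power at other reductions, 50,000 days.** 10%: 17%. 20%: 53%. 25%: 73%. These effects would therefore be missed about 83%, 47% and 27% of the time.

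**Days needed for the stated claims.** The required deaths in the comparison period are d1 = (1.96 + 0.842)² × (1 + RR) / (1 − RR)².

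- RR 0.99: about 156,200 deaths, or 41.7 million days per period (833 times 50,000).
- RR 0.98: about 38,850 deaths, or 10.4 million days per period (1,727 times 6,000).

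**Larger exposures.** The plan presents its day counts as very cautious, so larger ones were tried at 37.5 per 10,000. The detectable reductions are:

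- all four hospitals for 3 months (178,202 days per period): 15%
- half of all bed-days for 9 months (267,303): 12%
- all bed-days for 9 months in each arm (534,606, more than the design allows): 8.7%

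**Precision.** If the observed rate ratio were exactly 1.0, the 95% interval would be exp(±1.96 × √(2/187.5)) = 0.82 to 1.22 at 50,000 days, and exp(±1.96 × √(2/22.5)) = 0.56 to 1.79 at 6,000 days.

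**Absolute reading, per inpatient day.** The detectable reductions are 0.269 × 0.375% = 0.10 points and 0.679 × 0.375% = 0.25 points, so the two power sentences could hold if 1% and 2% meant percentage points. But one point per day is 1 / 0.375 = 2.7 times the entire daily death rate. It cannot then be smaller than a clinically meaningful difference.

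**The case against.** The strongest defence is that the authors meant absolute points per admission and wrote relative by mistake. The plan expects at least 2,000 admissions a month. If a period is one 3-month phase (an assumption), that is 6,000 admissions, and 187.5 deaths is 3.1% per admission. A two-proportion calculation then detects about 0.83 points, which is under 1%. In the same ratio, 6,000 days is 720 admissions and the detectable difference is about 2.1 points, close to 2% but not under it. With an assumed stay of 4 to 6 days instead, the figures are 0.40 to 0.60 and 1.0 to 1.5 points, and both bounds hold.

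This may well explain how the numbers arose, but it does not rescue the text. The plan says relative both times and works in inpatient days. On the per-admission scale the detectable reduction is still about 27% overall and 67% for a campus in relative terms. One point off 3.1% is a 32% relative reduction, so the plan would be treating the loss of nearly a third of deaths as clinically negligible.

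Three lesser points stand in part:

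- The 50,000 and 6,000 days are lower-end figures, so 27% and 68% describe the plan's stated case, not necessarily what the trial can detect. Exposure per arm is not given.
- The 6,000-day figure rests on a normal approximation with about 7 deaths in one period. The range of 66% to 71% across methods is the fairer statement.
- The effect of clustering depends on the contrast. Stable differences between units largely cancel in a before-after comparison within units, and matter more for active versus silent units. The documents give no intracluster correlation. Assumed design effects of 1.5, 2 and 3 would move 27% to 32%, 37% and 44%.

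**Conclusion.** The concern holds. From the plan's own inputs, the claimed power of at least 80% is about 5% in both cases, and the relative reductions that do have 80% power are about 27% and 68%, against the stated 1% and 2%. The figures assume equal periods, independent Poisson counts and two-sided alpha 0.05. No test, baseline rate or exposure examined brings the detectable difference near the stated values. The sufficiency conclusion fails whether the percentages are read as relative or absolute. What is shown is that the adequacy of the sample is unsupported. Whether it is inadequate cannot be judged until a clinically meaningful mortality difference is stated.

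Because this is the sole sample-size justification for a primary outcome, it must be corrected.

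**What to change.** 1. Replace the two power statements with: at 37.5 deaths per 10,000 inpatient days, two-sided alpha 0.05, equal periods and no clustering, 80% power is reached for a relative reduction of about 27% (rate ratio 0.73) with 50,000 days per period, and about 68% (rate ratio 0.32; 66% to 71% depending on method) with 6,000 days. Name the method used.
2. Delete the sentence on sufficient sample size, or re-justify it by stating a clinically meaningful relative mortality difference and comparing it with these figures.
3. Restate power for the contrast actually analysed (active versus silent, or versus baseline, over the phases pooled), at the expected exposure per arm and with an allowance for clustering by unit suited to that contrast.
4. Optionally, label campus-level mortality comparisons as descriptive.

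The cost is SAP wording and one recalculation, with no additional patients. The drawback is that the stated detectable difference becomes much less favourable.

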The CONCERN Early Warning System:

Study Protocol and Analysis Plan

NCT03911687

INVESTIGATORS

[name], RN and [name], RN

PROTOCOL TITLE

Communicating Narrative Concerns Entered by RNs (CONCERN): Clinical Decision Support Communication for Risky Patient States

FUNDING NINR

R01NR016941

VERSION DATE

November 11, 2016:

Table of Contents

Content	Pages
I. Original Study Protocol and Statistical Analysis Plan (submitted to/funded by NINR and IRB approved)	2-4

1. Original Study Protocol and Analysis Plan

Aim 3 below is focused on the CONCERN Early Warning Score Trial Design and Analysis Plan and is excerpted from R01 grant funded in 2017 (NINR 1R01NR016941, COmmunicating Narrative Concerns Entered by RNs (CONCERN): Clinical Decision Support Communication for Risky Patient States). Protocol below was IRB approved November 2016.

Aim 3. Evaluate the impact of the CONCERN SMARTapp notification system on patient outcomes, for the primary outcomes of in-hospital mortality and length of stay (LOS) and secondary outcomes of cardiac arrest, unanticipated transfers to the intensive care unit, and 30-day hospital readmission rates.

Table 1. Sample and Setting Calendar Year 2014 (all adult patients)

Site	Beds	Occupancy Rate	In-patient Mortality	30-day Readmit	CONCERN implementation processes
PHS-BWH	777	95%	1001	18%	
PHS-NWH	300	94%	312	10%	
NYP-CUMC	745	95%	1261	18%	
NYP-Allen	300	75%	98	10%	will use open source tools, APIs (application program interfaces), web services, and SMART tools developed at Harvard Medical School. The

need for site specific, local EHR configurations will be minimized using this approach. Our technology solution will allow for continuous refinement of algorithm, pushing out a new version every 3 months to provide consistent amount of time to evaluate and track outcomes for each version.

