CONCERN Intervention Trial Design will be a multiple time-series intervention (see Table 2). Please also refer to Table 1 for study sites and samples. Baseline data will be collected at all study sites. Silent release mode (no SMARTapp notification) will be used in non-equivalent control units and as a post-intervention unit control to evaluate if notifying clinicians can decrease rates of length of stay on non-ICU units and rates of 30-day hospital readmissions. In Table 2 the different versions indicate dynamic, adaptive functionality. The adaptive function utilizes [name] inpatient acuity calculation¹¹⁸ to determine if the pattern of nursing documentation has changed. We have built in time for a "burn-in" phase to evaluate adoption and adaptation to our algorithm.

Table 2. Trial Design with Multiple Time-series Intervention

Study Arm	Site	Pre-intervention (6 months)	Phase 1 (3 months) [burn-in phase]	Phase 2a (3 months)	Phase 2b (3 months)	Phase 3 (3 months)
Control Groups	Site A	B	XX	V1 silent	V2 silent	V3 silent
	Site B	B		V1 silent	V2 silent	V3 silent
	Site A	B		V1 active	V2 active	V3 active
	Site B	B		V1 active	V2 active	V3 active

B = baseline data; none = no intervention; silent = CONCERN App will function but will not display to clinician, active = CONCERN App will display to clinician. V1=version 1; V2=version 2 refined based on continuous monitoring of data

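### Campus-level mortality comparisons are presented as powered at an unadjusted two-sided 0.05, with no stated status or multiplicity rule, and the power claim fails on the plan's own figures

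*Combined protocol and SAP*

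**What the plan says.** All of this is in the combined protocol and SAP, Aim 3.

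- **Significance level.** The paragraph on trial data collection and analysis states: "All power calculations were based on 2-sided tests with alpha = 0.05".
- **Overall power.** "Using a very conservative number of total 50,000 inpatient days in each intervention period", the plan says, "we will have at least 80% statistical power to detect a difference of less than 1% relative difference in mortality rates".
- **Campus power.** "When examined by different campuses, using a very conservative value of inpatient days in one campus of 6000 inpatient days in each intervention period", the plan says, "we will have at least 80% statistical power to detect a difference of less than 2% relative difference in mortality rates".
- **Event rate.** The plan assumes "mean mortality rates of 37.5 deaths per 10,000 inpatient days (ranging from 11.9 to 48.8), see Table 1".
- **Number of campuses.** The trial design paragraph says "Please also refer to Table 1 for study sites and samples". Table 1 lists four hospitals. Table 2, the design table, shows only Site A and Site B.
- **Planned analysis.** Each primary outcome (in-hospital mortality and length of stay) goes into a generalized linear mixed model that pools the sites. A unit-level interrupted time series is added. Number needed to treat is to be given for each site, but the outcomes listed for it are length of stay and readmission, not mortality.

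The text does not say whether campus-level mortality results are confirmatory or exploratory. It also gives no multiplicity rule and no test of whether the effect differs between campuses.

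**The concern.** Mortality is a primary outcome. A separate power statement at the full 0.05 tells readers that a campus result can stand on its own, and nothing else in the plan corrects that impression. Two things are at stake.

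1. **Error rate.** After a null pooled result, one campus could be reported as showing benefit or harm, with more than a nominal chance of error across the set of campuses. If one campus were significant and another not, readers would tend to see a difference in effect, which separate p-values do not test.
2. **Credibility of a significant campus result.** If the true campus-level power is very low, a significant campus result is likely to be either false or a large overestimate, while the plan tells the reader that such comparisons are well powered.

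**Working it through.** **Inputs.** Two-sided alpha 0.05; 6,000 inpatient days per campus per period; 37.5 deaths per 10,000 days (range 11.9 to 48.8); a 2% relative difference. All come from the data collection and analysis paragraph. The hospital count (four) is from Table 1 and the site count (two) from Table 2.

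**Step 1. What the mortality range refers to.** Rate = deaths / (beds × occupancy × 365), from Table 1:

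| Hospital | Inpatient days per year | Deaths | Per 10,000 days |
|---|---|---|---|
| PHS-BWH | 777 × 0.95 × 365 = 269,425 | 1,001 | 37.2 |
| PHS-NWH | 300 × 0.94 × 365 = 102,930 | 312 | 30.3 |
| NYP-CUMC | 745 × 0.95 × 365 = 258,329 | 1,261 | 48.8 |
| NYP-Allen | 300 × 0.75 × 365 = 82,125 | 98 | 11.9 |
| All | 712,809 | 2,672 | 37.5 |

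The plan's mean and both ends of its range reproduce, so the power paragraph draws on the four Table 1 hospitals.

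**Step 2. The plan's campus power figure.** Compare two periods of n = 6,000 days each, treating days as independent.

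- p1 = 0.00375 (22.5 expected deaths); p2 = 0.98 × 0.00375 = 0.003675; difference = 0.000075.
- SE = √{[0.00375 × 0.99625 + 0.003675 × 0.996325] / 6,000} = 0.00111.
- Standardised difference = 0.000075 / 0.00111 = 0.068.
- Power in the favourable direction = Φ(0.068 − 1.96) = 0.029. The wrong direction adds Φ(−0.068 − 1.96) = 0.021. The two-sided total is 0.051.

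The stated figure of at least 80% does not reproduce. Solving the same formula the other way:

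- The relative reduction detectable with 80% power is about 68%, or 0.25 percentage points. At 48.8 per 10,000 it is about 61%. At 11.9 per 10,000 (7.1 expected deaths), even near-elimination of deaths does not reach 80% by this approximation.
- Days per period needed for a 2% relative reduction: (1.96 + 0.842)² × [p1(1 − p1) + p2(1 − p2)] / 0.000075² ≈ 10.3 million. That is about 14.5 times the yearly inpatient days of all four hospitals (10.3 million / 712,809).

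The pooled sentence has the same fault. At 50,000 days, favourable-direction power for a 1% relative reduction is about 3%, and the reduction detectable with 80% power is about 27%.

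The 1% and 2% limits are met only if read as absolute percentage points, since the detectable reductions are 0.10 and 0.25 points. The plan says relative, however, and a fall of 2 points cannot occur from a rate of 0.375% per day.

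**Step 3. Error rate across campuses.** One contrast per campus, different patients at each, no true effect. A two-sided 0.05 test spends 0.025 in the benefit direction.

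| Campuses tested | Any false-significant campus | Any false benefit |
|---|---|---|
| Four (Table 1), independent | 1 − 0.95⁴ = 18.5% | 1 − 0.975⁴ = 9.6% |
| Four, bound under any dependence | 4 × 0.05 = 20% | 4 × 0.025 = 10% |
| Two (Table 2), independent | 1 − 0.95² = 9.75% | 1 − 0.975² = 4.9% |

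The reference values for a single test are 5% and 2.5%.

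**The case against.** **The campus sentence defines no hypothesis.** It is a power statement in a grant excerpt and may be there only to show feasibility. The primary model pools the sites. This stands: a reader might infer that mortality will be tested campus by campus as a confirmatory claim, and the documents do not say so. What they support is that the status of campus results is left open.

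**The error rate is easy to overstate.** A reader might take 18.5% as the chance of falsely declaring that CONCERN works at some campus. It is not, because it counts false harm as well; the false-benefit figure is 9.6%. It also assumes four tests, while Table 2 shows two sites. Both corrections stand and are carried in the figures above.

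**Testing in each phase.** The phrase about each intervention period might suggest a separate test per campus per phase, and so many more tests. The same phrase appears in the pooled power sentence, where it only describes the person-time assumed. No section plans phase-by-phase campus tests, so no such figure is given here.

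**6,000 days is described as conservative.** It is: the busiest Table 1 hospital has about 269,425 / 4 = 67,356 days in three months. At that size and 37.5 deaths per 10,000 days, the standardised difference for a 2% relative reduction is 0.226, and favourable-direction power is Φ(0.226 − 1.96) = 4.1%. The objection does not rescue the claim.

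**Conclusion.** The point holds in this form: the plan offers campus-level mortality comparisons as adequately powered at an unadjusted 0.05, gives them no status or multiplicity rule, and the power claim is not supported by its own inputs.

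The inflation is moderate and conditional on campuses actually being tested separately. It is about 18.5% for any false-significant campus and 9.6% for false benefit with four campuses, or 9.75% and 4.9% with two. These figures cover one contrast on one outcome, with independent campuses.

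The power shortfall is large and does not depend on how many campuses are tested: about 3% in the favourable direction (5% two-sided) against a claimed 80%, with a detectable reduction of about 68% against a claimed 2%. The calculation treats inpatient days as independent and uses a normal approximation, which is rough at about 22 deaths per period. Positive clustering within units would lower power further.

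The documents do not support saying that a campus-level efficacy claim is planned.

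**What to change.** 1. **Power.** Remove the campus power sentence from the sample-size justification, or restate it with the detectable difference that 6,000 days provides and say whether it is relative or absolute. Correct the pooled sentence in the same way.
2. **Status.** State that campus-level mortality effects are exploratory and will be shown as estimates with 95% intervals, without significance claims.
3. **Differences between campuses.** Rest any such statement on one campus-by-display-mode (silent or active) interaction test in the mixed model already planned. State that a non-significant interaction will not be read as evidence of equal effects, since that test will also have little power.
4. **Campus count.** Say whether a campus means one of the four Table 1 hospitals or one of the two Table 2 sites.

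The cost is SAP wording and one model term; data collection and the pooled primary analysis do not change. The small downside is giving up stand-alone campus claims. If the sponsor wants to keep them, Bonferroni at 0.05 / 4 = 0.0125 per campus holds the error to 1 − 0.9875⁴ = 4.9% in either direction. It raises the detectable reduction from about 68% to about 78%, so it controls the error rate but does not make the campus tests informative.

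### The by-campus claim of 80% power for a relative mortality difference under 2% is wrong at every campus, and no single replacement figure would serve campuses whose death rates differ four-fold

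*Combined protocol and SAP*

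**What the plan says.** The power statement is in the combined protocol and SAP, Aim 3, in the paragraph on trial data collection and analysis.

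- **Comparison:** "comparison of mortality rates between the intervention and non-intervention periods and between silent and active model periods". No test is named.
- **Error rate:** "All power calculations were based on 2-sided tests with alpha = 0.05".
- **Rates:** "mean mortality rates of 37.5 deaths per 10,000 inpatient days (ranging from 11.9 to 48.8), see Table 1".
- **By-campus claim:** "using a very conservative value of inpatient days in one campus of 6000 inpatient days in each intervention period", the plan states that "we will have at least 80% statistical power to detect a difference of less than 2% relative difference in mortality rates".

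The by-campus sentence does not say which death rate it used. Table 1 gives beds, occupancy, deaths and readmission for each campus in 2014, for example "NYP-Allen 300 75% 98 10" and "NYP-CUMC 745 95% 1261 18" (last figure a percentage). It prints death counts, not rates.

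**The concern.** With rare events, power depends on the expected number of deaths, not on inpatient days. A claim stated in days holds for a campus only at that campus's death rate. The plan prints a range of rates with a ratio of 48.8/11.9 = 4.1, yet gives one claim for any campus.

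Two things are at stake. First, mortality is a primary outcome, and a reader who trusts the 80% figure would take a null campus result as evidence that CONCERN does not work there, or that campuses differ. Second, correcting only the 2%, using the mean rate, would leave a figure that is still wrong for the low-mortality campuses.

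**Working it through.** **Inputs.** Two-sided alpha 0.05, 80% power and 6,000 days in each of two periods (Aim 3 power text); beds, occupancy and deaths (Table 1). Clustering by unit and time trends are ignored.

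**Step 1: campus rates.** Rate = deaths / (beds × occupancy × 365).

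| Campus | Inpatient days per year | Deaths | Per 10,000 days | Expected deaths in 6,000 days |
|---|---|---|---|---|
| BWH | 777 × 0.95 × 365 = 269,425 | 1001 | 37.2 | 22.3 |
| NWH | 300 × 0.94 × 365 = 102,930 | 312 | 30.3 | 18.2 |
| CUMC | 745 × 0.95 × 365 = 258,329 | 1261 | 48.8 | 29.3 |
| Allen | 300 × 0.75 × 365 = 82,125 | 98 | 11.9 | 7.2 (7.1 from the printed 11.9) |

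Overall: 2,672 / 712,809 = 37.5. This reproduces the plan's mean and both ends of its range, so the printed range is the range across campuses.

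**Step 2: the plan's own figure.** For deaths per inpatient day, power = Φ[(|p1 − p2|√n − 1.96√(2p̄(1 − p̄))) / √(p1(1 − p1) + p2(1 − p2))], where p̄ is the mean of p1 and p2. For a 2% relative reduction with n = 6,000:

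- at 11.9 per 10,000: (0.00184 − 1.96 × 0.04851) / 0.04851 = −1.92, power 2.7%;
- at 37.5: 2.9%;
- at 48.8: 3.0%.

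Counting rejections in both directions gives about 5%, which is the false-positive rate. The days needed per period for 80% power are about 32.6 million at 11.9 and 7.9 million at 48.8. The 80% figure does not reproduce. Only reading 2% as an absolute change of 2 percentage points per inpatient day gives power above 80%; the text says relative, and a fall of that size is impossible from rates of 0.12% to 0.49%.

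**Step 3: detectable reduction by campus.** For small rates the formula reduces to λq² = (1.96 + 0.84)²(2 − q) = 7.85(2 − q), where λ is expected deaths per period and q is the relative reduction.

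- BWH, λ = 22.3: q = 68%
- NWH, λ = 18.2: q = 74%
- CUMC, λ = 29.3: q = 61%
- Allen, λ = 7.1 to 7.2: no solution, because q = 1 already needs λ = 7.85 (about 6,590 days)

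**Step 4: Allen, with the test named.** At about 7 deaths against 0 the normal approximation is rough, so power was also enumerated over Poisson counts with λ = 7.14.

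| Reduction at Allen | Exact conditional | Mid-p | Uncorrected score | Normal approximation |
|---|---|---|---|---|
| 50% | 12% | 17% | 17% | 19% |
| 68% | 24% | 33% | 33% | 35% |
| 95% | 62% | 74% | 80% | 70% |
| 98% | 67% | 80% | 87% | 74% |
| 100% | 72% | 84% | 93% | 76% |

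With no deaths in the active period, the exact test needs at least 6 in the comparison period, mid-p needs 5 and the score test needs 4. Actual sizes are 2.7%, 4.5% and 4.6%. A likelihood-ratio test has 79% power at a 90% reduction, but its size is 6.1%.

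**Step 5: would one corrected figure do?** The mean rate of 37.5 gives λ = 22.5 and q = 68%. At NWH, that reduction has 71% power by the normal approximation. At Allen it has 24% to 35% (table above). Allen would need 22.5 / 0.00119 = about 18,900 days per period to match.

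**The case against.** **Allen is not an impossibility.** A reader might infer that no mortality reduction at Allen can reach 80% power, or that a test there could not be positive. The documents do not support this. They name no test, and two tests that hold their size near 5% do reach 80%, at reductions of about 95% and 98%. Even where 80% is not reached, 72% to 76% power is far from zero. What stands is that Allen has 80% power, at best, for near-complete elimination of deaths.

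**Separate campus tests are not specified.** A reader might also infer that stand-alone campus mortality tests are planned. The text only refers to examining mortality by campus, within the power statement. The stated model combines sites, and the one per-site output it specifies, the Number Needed to Treat, is for length of stay and readmission. The harm from misreading a campus p-value is therefore conditional on such an examination being made.

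**6,000 days is a stated floor.** This is fair: the plan calls it very conservative and does not name Allen. It is nevertheless the only basis given for the 80%. If every Allen unit took part (an assumption), three months would give about 20,500 days and a detectable reduction of about 66%. With an even split between arms, it would be about 86% per three-month phase (10,270 days, 12 deaths) and 56% over nine months (37 deaths). A comparison period of 12,000 days against 6,000 would bring complete elimination at Allen to 84% by the normal approximation. None of these approaches 2%.

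**It is part of correcting the 2%.** Partly so: the 2% claim fails everywhere, and that is the larger error. But step 5 shows that correcting it with the mean rate leaves Allen and NWH misstated.

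**Conclusion.** The by-campus power sentence is wrong as written. At 6,000 days per period, power for a 2% relative reduction is about 3% at each campus, against the 80% claimed. The reductions detectable with 80% power are about 61% (CUMC), 68% (BWH) and 74% (NWH). At Allen, 80% is reached only for near-complete elimination of deaths or for no reduction at all, depending on the test.

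This rests on 2014 rates derived from Table 1, equal exposure in two periods, a two-sided 0.05 test and independent inpatient days. Clustering by unit or positive autocorrelation would generally lower power further. The failure of the 2% claim and the four-fold spread in rates do not depend on the choice of test; only the exact position of Allen does.

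**What to change.** 1. Delete the single by-campus power sentence. Print the detectable relative difference for each campus from its own Table 1 rate, naming the test and the days assumed.
2. State that at 6,000 days per period Allen has 80% power only for near-complete elimination of deaths, or for no reduction, depending on the test named.
3. If mortality is examined by campus, do it through a term in the planned mixed model for the interaction of campus with display (active versus silent). Report campus estimates with intervals, and state that a non-significant result at one campus will not be read as no effect there.

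The cost is a rewritten power paragraph and one model term; no new data are needed. The downside is that the stated by-campus power becomes much less favourable.
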